## **Intervention including time plan**

A team consisting of one of the mentors from Fitforlife, a health pedagogic, and one or two from the research group will come to each included open care unit.

Day 1; Upstart meeting led by a research group member.

Day 1-4; Education of the new mentors led by the health pedagogic assisted by mentor(s) from Fitforlife pilot study.

Day 1-5; Baseline examinations (see above for data collection tools) of all the potential participants by the local contact person(s).

Day 5-14; Start of the training. Initially supported by the health pedagogic and the mentor(s) from Fitforlife pilot study.

Day 14-70: Training sessions led by the local mentors. Supported by phone and online by the health pedagogics and the mentors from Fitforlife. During this time 1-3 visit(s) from the health pedagogic to each mentor during a training session.

Day 70-75: Follow up assessments by the local contact person.

#### *Measurements during the intervention*

Compliance will be measured by the local coordinators. In a subgroup objective measures of physical activity using simple accelerometers will be performed.

Before and after each training session the participant will be asked to answer simple App based questions - "How do you feel" (happy, tired etc).

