### **Preliminary results Fitforlife pilot study**

During 2015-2016, 99 participants were included. A majority were males (60 persons) and the mean age was 28.2 years. The study was originally designed as a waiting list study but due to

problems with the open care units this turned out to be impossible. Of the 99 persons 39 did not attend any sessions, the rest attended between 1-52 sessions, mean 13.1(SD 12.1). Trailmaking A test time (visual attention) improved 8.5 seconds (SD 20.4) in those that attended >1 session and 5.4 (SD 6.5) in those that did not attend. Trailmaking B, (visual attention and task shifting), improved 10.4 seconds (SD 42.8) in attenders versus 4.6 (SD 31.7) in non-attenders.

Camberwell assessment of need showed that at the initial examination 33 persons reported difficulties with social contacts while at the end of the intervention 17 of those reported no problems. Likewise, 24 persons reported problems with close relations at baseline while 11 of them reported no problem at the end. In the proposed study this will be measured in a more extensive way. During an open house for participants and relatives there were reports about improvement in daily life such as "started to care about his looks", "cleans his room". During spring 2017 the cognitive tests will be analysed and linked with inflammatory markers. The study has given us experience on how to organise exercise for persons with psychosis. After the first wave four participants were educated as peer mentors. At least one peer-mentor was present in all sessions in wave two and three. The peer mentors were responsible for organizing parts of the sessions under supervision of educated trainers. Since the study finished the mentors have worked as peer mentor trainers, offering sessions to patients at an open care unit for FEP. The staff promote the sessions during their meetings with their patients and discussion about physical activity levels is a part of all patients' individual care programme.

**Study objectives:** See separate information

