## **Methodology**

Study design: Non randomized open trial.

*Study population:* Patients affected by psychosis at open care psychiatric units who are responsible for taking care of psychosis in Sweden.

*Sample size:* Our aim is to recruit 300 patients including mentors at each unit.

*Variables list including data collection tools:*

1. From the medical records: age, gender, diagnosis, time of first contact with psychiatry, medication
  - App questions on overall function using WHODAS 2.0
  - App question on social network: qualitative and quantitative
  - App questions: smoking, alcohol consumption and illicit drug use
  - Cognitive tests: Cogstate (performed at a computer) and Trail making A and B
  - Submaximal fitness test: Åstrand
  - Physical activity pattern, including sedentary time, low-intensity physical activity and exercise, assessed by a simple accelerometer on a subsample.
  - Body measurements: length, weight, hip-waist measure, blood pressure.
  - Blood samples: Blood lipids, HBA1C, TNFalfa, CRP, Il-6

*Plan of analyses:* See separate information

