#### *Long term follow-up- 12 months*

The participants will be followed using medical records.

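### No variable in the supplied protocol or SAP records harm or the reason for stopping, so the planned comparison by attendance cannot be checked for reverse causation

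*Protocol*

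**What the plan says.** The data collection is described in three parts of the protocol.

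- **Methodology, variables list.** The items from records are five: "From the medical records: age, gender, diagnosis, time of first contact with psychiatry, medication". The remaining items are App questions (including "App questions on overall function using WHODAS 2.0"), cognitive tests, a fitness test, activity pattern in a subsample, body measurements and blood samples. There is no item for injury, adverse event, relapse, admission, withdrawal or reason for stopping, and no psychotic-symptom scale.
- **Measurements during the intervention.** Attendance is logged at each unit: "Compliance will be measured by the local coordinators". Accelerometers are worn by only some of the participants. The one self-report is the mood question: "Before and after each training session the participant will be asked to answer simple App based questions".
- **After training.** The time plan has "Day 70-75: Follow up assessments by the local contact person". The 12-month section says "The participants will be followed using medical records", without naming what will be extracted.

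The SAP divides participants into quartiles by number of sessions attended and compares the groups by ANCOVA with the baseline score as covariate. It plans no analysis of harm, dropout or reasons for stopping. The protocol refers elsewhere for study objectives and ethical permission, and that material is not in the supplied text.

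**The concern.** Two things are at stake.

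The first is the harm estimate. The protocol presents patient-led exercise as a new concept, in a population whose background section describes frequent relapse and high rates of cardiovascular disease. A unit deciding whether to adopt the model would want to know how many people were injured or got worse. As planned, the trial could report benefit with no direct count of either.

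The second is the between-group comparison, which rests on attendance, a variable that arises after baseline. If some people attend little because they were injured or got worse, their poor outcomes sit in the lower-attendance groups and the higher groups look better by contrast. The reason for stopping is the variable needed to judge how far this happened, and it is not collected.

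**Working it through.** The plan states no figure on this point, so there is none to reproduce. The check has three steps.

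**1. What each source could reveal about a person who stops because of injury or worsening.**

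| Source | Shows the stop? | Shows the harm? | Shows the reason? |
|---|---|---|---|
| Compliance record | Yes | No | No reason item mentioned |
| Session-tied mood question | Ends when attendance ends | Not a harm question, even for attenders | No |
| Accelerometer | Perhaps, as lower activity, subgroup only | No | No |
| Day 70-75 assessment | No | Indirectly, for example by WHODAS 2.0, if the person returns | No |
| 12-month medical records | Not stated | Possibly, if documented and extracted | Not stated |

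No source records harm directly and none is stated to record the reason. The SAP also speaks of main-outcome data up to 6 months, but the protocol's time plan has no visit then, so this adds no identifiable source.

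**2. Effect on the attendance comparison.** Suppose training has no effect. Let a group of size m contain k people who stopped because they got worse, each by d points on the outcome after baseline. The mean change of that group is then shifted by k × d / m. With 300 people in equal quartiles, m = 300/4 = 75, so the shift is k × d / 75. ANCOVA adjusts for the score before training. The k people need not differ from the others at baseline, because their worsening came later, so the covariate does not absorb the shift. The documents give neither k nor d, so the bias cannot be sized. Its direction is in favour of attendance.

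**3. Scale of non-attendance.** Inputs: "Of the 99 persons 39 did not attend any sessions" (pilot results) and a target of 300 (Methodology).

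- Share: p = 39/99 = 0.394.
- Wilson 95% interval, with n = 99 and z = 1.96: centre = (p + z²/2n) / (1 + z²/n) = 0.4133/1.0388 = 0.398. Half-width = z × √(p(1−p)/n + z²/4n²) / (1 + z²/n) = 0.0982/1.0388 = 0.0945. The interval is 30.3% to 49.2%.
- Applied to 300: 300 × 0.394 = 118, with range 300 × 0.303 = 91 to 300 × 0.492 = 148.

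These are people who would never meet a session-tied question. They are not a count of people harmed. Someone who never came cannot have been injured by training, although worsening illness may have kept them away. People who start and then stop would add to the 118, but the documents do not give their number. The 300 includes mentors, who lead sessions, so the pilot share may be somewhat high for this sample.

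**The case against.** The strongest reply is that several routes remain open. Compliance records show that a person stopped. The Day 70-75 assessment is not restricted to those still attending, and measures such as WHODAS 2.0, fitness and body measurements can show deterioration. The participants are patients of the open care units, so a serious event may well be in their records, and the 12-month follow-up covers participants without regard to attendance. The mood question reads as a measure of each session's immediate effect, for which asking at sessions is natural. It was never described as safety monitoring. Finally, a safety procedure may exist in the material the protocol refers to elsewhere.

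Much of this stands. A reader might infer that anyone harmed who stops attending leaves no trace in the trial. The documents do not support that, for the reasons just given. A reader might also infer that attenders are monitored for harm and only those who stop are missed. That is not supported either, because attenders are not asked about harm.

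The reply does not remove the narrower gap. A lower WHODAS-rated function at Day 70-75 does not say whether an injury or relapse occurred, or whether it preceded the stopping. The record follow-up helps only if the events are named and extracted. A safety procedure held elsewhere would not by itself put a harm or reason variable into this data list or this analysis.

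**Conclusion.** The point holds in limited form. In the supplied protocol and SAP, no variable records injury, worsening or reason for stopping for any participant, and harm can be seen only indirectly. As a result the comparison by attendance is open to reverse causation that baseline adjustment cannot remove, and without recorded reasons it cannot be examined afterwards.

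The number harmed and the size of the bias are unknown. The figure of about 118 (91 to 148) only indicates how many might receive no session-tied question, and it assumes that the pilot's attendance carries over to the new units. The finding depends on what the supplied text contains, and a safety procedure in the unseen material would soften the first half. This is a cheap improvement and not a fatal defect.

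**What to change.** 1. **Day 70-75 follow-up.** Ask every enrolled person, whatever their attendance, two App items: any injury or worsening since baseline, with whether the person links it to training; and the main reason for missing or stopping sessions. Record the event and the attribution separately, so that the count does not depend on the participant's own view of cause.
2. **Medical-record follow-up.** Name the events to extract (for example injury, relapse, admission), so that people who do not return at Day 70-75 are covered.
3. **SAP.** Add one table with the number of people with any event and an exact 95% CI, the number not responding, and the reasons for missing or stopping by attendance group. State that the attendance comparison is open to reverse causation and should be read as an association.

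The cost is about a minute of participant time, a little more record extraction and one table. The self-report will carry recall error over some ten weeks (70/7 = 10), in a population that the protocol describes as having memory impairment, which is a further reason to use the records as well. The report may also turn out less favourable.

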#### *Long term follow-up- 12 months*

The participants will be followed using medical records.

#### **Strengths and limitations**

Largest study of physical exercise in psychosis. Using an entirely new concept, patients lead physical exercise.

Not randomized due to practical issues. Impossible to randomize patients within a unit, many ongoing group activities. Differences between units in care programme large making cluster randomization difficult.

**Ethical permission:** See separate information

### **Statistical analysis plan**

Baseline descriptions will be presented and used in the different analyses to see if gender, duration of psychosis, neuroleptics affects the different outcomes.

The main outcome social function will be analyzed using  $\chi^2$  tests and analysis of variance for categorical outcomes using data from baseline to 6 months. Pre- to post-intervention (within-group) analyses will be performed using paired-sample *t*tests, with effect sizes (Hedges' *g*) calculated for statistically significant values. The participants will be divided according to attended number of training sessions. This will be done in quartiles and used to look at between group differences (analysis of covariance- ANCOVA). A sub analysis will be done including those with accelerometer data from the entire study period. Baseline score will be included as covariates in each model.

Parametric test assumptions will be checked before running all analyses. Normality will be assessed using the Shapiro–Wilks test and normal probability plot, and homogeneity of variance using Levene's test. For analyses involving unequal sample sizes, Welch's test might be considered. Similar procedures will be used when analyzing blood samples, inflammatory and metabolic markers as well as cognitive test data. Normative data from the cog state data base will be used for comparison. Multilevel analysis will be used taking into account the included open care units.

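### The SAP analyses the main outcome to 6 months, but the protocol's only post-baseline participant assessment is at Day 70-75

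*SAP*

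**What the plan says.** The SAP's second paragraph names social function as the main outcome and says that it will be analysed with χ² "tests and analysis of variance for categorical outcomes using data from baseline to 6 months". The next sentence plans paired t tests of change from before to after the intervention.

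The protocol section Intervention including time plan sets baseline examinations at Day 1-5. Training starts between Day 5 and Day 14 and continues as "Day 14-70: Training sessions led by the local mentors". The last entry is "Day 70-75: Follow up assessments by the local contact person".

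Two other protocol sections describe data collected after baseline:

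- Measurements during the intervention covers compliance, accelerometers in a subgroup, and mood questions: "Before and after each training session the participant will be asked to answer simple App based questions".
- Long term follow-up- 12 months says only "The participants will be followed using medical records".

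In the variables list under Methodology, the items closest to social function are app items: "App questions on overall function using WHODAS 2.0" and a question on social network. The medical-record line reads "From the medical records: age, gender, diagnosis, time of first contact with psychiatry, medication".

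**The concern.** The SAP gives its main outcome a time point at which the protocol schedules no participant assessment. In an open, non-randomised study that relies on before-after change, the time point is a large part of the claim. An improvement at the end of ten weeks of organised training is one finding. An improvement still present more than three months after that training was scheduled to end is a different and stronger one.

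Consecutive SAP sentences also point to different times, since the paired tests fit Day 70-75 and the main-outcome sentence does not. The analyst would have to choose. If 6 months was intended, an app questionnaire that is not scheduled in time cannot be collected afterwards.

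**Working it through.** The plan gives no figure to reproduce here. The check sets the SAP's time point against every data source in the protocol, then measures the gap.

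**Could any listed source supply social function at 6 months?**

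| Source (protocol section) | Timing | Social-function measure stated? |
|---|---|---|
| Baseline examinations (time plan) | Day 1-5 | Yes, through the app items in the variables list |
| Follow-up assessments (time plan) | Day 70-75 | Not itemised; taken to repeat the baseline tools |
| Compliance, accelerometers, mood questions (Measurements during the intervention) | During training, which is scheduled to Day 70 | No |
| Medical records (Long term follow-up) | 12 months | Content not stated; the record line in the variables list has no function measure, though that list is not tied to this follow-up |

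No row specifies social function at 6 months.

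**How large is the gap?** Inputs are baseline at Day 1-5 and follow-up at Day 70-75 (protocol time plan), and 6 months (SAP). Six months is taken as 365.25 / 2 = 182.6 days.

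- Shortest scheduled interval: 70 − 5 = 65 days; 65 / 182.6 = 36% of 6 months.
- Longest scheduled interval: 75 − 1 = 74 days; 74 / 182.6 = 41% of 6 months.
- Gap from each participant's own baseline: 182.6 − 74 = 108.6 days to 182.6 − 65 = 117.6 days, so about 109-118 days.
- As a share of 6 months: 108.6 / 182.6 = 59% to 117.6 / 182.6 = 64%.
- Counted from Day 0 instead: 183 − 75 = 108 days to 183 − 70 = 113 days.

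The SAP's time point is 182.6 / 74 = 2.5 to 182.6 / 65 = 2.8 times the scheduled interval. Rounding or a visit window does not explain a difference of that size.

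**The case against.** Four arguments can be made for the plan.

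1. The SAP phrase could describe a data window and not a fixed time point. Day 70-75 lies inside that window, so the analysis could be run. This reading is possible, but nothing is scheduled between Day 75 and 6 months. The wording would still attach a 6-month label to a result from about ten weeks, and the SAP would not fix the time of its main outcome.

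2. A 12-month record follow-up passes through month 6, and its content is not described. This part stands as a limit on the claim. The documents show that no 6-month social-function assessment is specified; they do not prove that the records could hold nothing relevant.

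3. The study objectives are in separate information that was not available, and the time plan is not presented as a complete assessment schedule. A 6-month time point may be defined elsewhere. That could show which text was intended, but the protocol and the SAP would still disagree as written.

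4. Neither document says which instrument measures social function, and the Day 70-75 entry lists no tools. Reading that follow-up as a repeat of the baseline tools is an assumption. It is the natural one, and the SAP's own paired before-after tests need it.

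The gap in days measures mislabelling in time. It does not measure bias or loss of power, and the harm to readers arises only if Day 70-75 data are reported under the SAP's wording.

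**Conclusion.** The inconsistency is real and concerns the main outcome, so it must be fixed. The only post-baseline participant assessment in the time plan comes 65-74 days after baseline, 109-118 days before the SAP's time point counted from each participant's own baseline. Confidence is high that the two documents conflict. They do not show which one is in error.

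The conclusion rests on three assumptions: 6 months means about 182.6 days, the Day 70-75 follow-up repeats the baseline tools, and the unseen separate information adds no 6-month assessment.

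**What to change.** Settle on one main time point and state it in both documents.

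- **Schedule as it stands.** In the SAP's main-outcome sentence, replace the 6-month period with the interval from baseline to the Day 70-75 follow-up, and limit the main conclusion to the end of the scheduled training period. In the same edit, name the social-function instrument and confirm in the time plan that it is repeated at Day 70-75. The main change is one SAP sentence; the price is a narrower claim.
- **If 6 months is intended.** Keep the SAP's time point and add a 6-month assessment to the protocol's time plan, with its window and instrument. The existing app questions could serve. This needs a short protocol amendment with whatever ethical approval applies, and one more questionnaire round. The downsides are added burden on participants and likely dropout between Day 75 and 6 months, for which the documents give no figure.

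The first option is enough to remove the contradiction.

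### The SAP's main-outcome sentence names a 6-month time point that is not scheduled and a test that does not suit its stated outcome type; of the two distinct contrasts that follow, neither is primary

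*SAP*

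**What the plan says.** The SAP (Statistical analysis plan, second paragraph) calls social function the main outcome and assigns it chi-square "tests and analysis of variance for categorical outcomes using data from baseline to 6 months". The same paragraph continues with "Pre- to post-intervention (within-group) analyses will be performed using paired-sample" t-tests. It then divides participants by number of sessions attended: "This will be done in quartiles and used to look at between group differences", by ANCOVA. It adds: "Baseline score will be included as covariates in each model". The third paragraph deals with assumption checks, then says "Similar procedures will be used when analyzing blood samples, inflammatory and metabolic markers as well as cognitive test data", and ends: "Multilevel analysis will be used taking into account the included open care units". One analysis, on participants with accelerometer data, is called a sub-analysis. No other analysis is ranked, and no significance level is given.

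The protocol (Intervention including time plan) puts baseline examinations at day 1-5 and follow-up assessments at day 70-75. Its section on long-term follow-up gives 12 months, from medical records. Its Methodology section refers the plan of analyses to separate information, so the protocol does not settle the matter.

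**The concern.** The sentence that should fix the main analysis cannot be carried out as written. It points to a time at which no assessment is scheduled, and it pairs analysis of variance with a categorical outcome.

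The sentences after it offer two contrasts without ranking them. The pre-post test asks whether the average participant changed. The attendance-quartile ANCOVA asks whether people who came more often ended up better than people who came less, given where they started. The trial is non-randomised and open, with no control arm described, so the choice between these questions largely determines what may be claimed. If the choice stays open until results are seen, a favourable answer to either can become the headline.

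**Working it through.** **1. Time point.** Six months is about 6 × 30.44 = 183 days. The scheduled follow-up assessment ends at day 75, or 75/30.44 = 2.5 months. The gap is about 183 − 75 = 108 days. The 12-month records follow-up spans month 6, but no assessment of participants is planned then. This contradiction needs no assumption.

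**2. Method against outcome type.** Analysis of variance models the mean of a continuous response. If the sentence means chi-square for categories and analysis of variance for scores, it does not say so. A chi-square test of a contingency table has no place for a baseline covariate or a unit effect, yet the SAP calls for both.

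**3. Two unranked contrasts.** Assume a two-sided 0.05 for each (the documents give no level), n=300 from the protocol's recruitment aim, independent participants, and attendance unrelated to outcome. If the two tests were independent, the chance of at least one false positive would be 1 − 0.95² = 0.0975. Simulating null trials with a paired t-test and a four-group ANCOVA adjusted for baseline, at within-person correlations of 0.3, 0.5 and 0.7, gives 9-10% throughout. One named primary contrast would hold it at 5%.

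**4. Illustration from the pilot.** The protocol reports that Trailmaking A time "improved 8.5 seconds (SD 20.4) in those that attended >1 session and 5.4 (SD 6.5) in those that did not attend". It also says "Of the 99 persons 39 did not attend any sessions", so attenders number at most 99 − 39 = 60. The numbers retested are not given. If 60 and 39 were retested:

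- Attenders, pre-post: t = 8.5/(20.4/√60) = 3.23, p = 0.002.
- Non-attenders, pre-post: t = 5.4/(6.5/√39) = 5.19, p < 0.001.
- Between groups (Welch): difference 8.5 − 5.4 = 3.1 s; SE = √(20.4²/60 + 6.5²/39) = 2.83; t = 1.09 on 76 df; p = 0.28; 95% CI −2.5 to 8.7 s.

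If about half were retested (30 and 20), the p values are 0.03, 0.001 and 0.44. The attender result depends on the number retested: n=25 gives p = 0.048, n=24 gives 0.053 and n=20 gives 0.078.

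Trailmaking B does not show this split. At the same upper-bound numbers, its p values are 0.06, 0.37 and 0.44.

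**The case against.** The strongest defence is that this is a short, pragmatic plan that already contains what is needed: paired analysis, baseline adjustment and a multilevel model for units. The only sentence naming the main outcome can be taken as the de facto main analysis, loosely worded. That defence has force, and it rules out several stronger readings that a reader might infer.

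- **That the SAP plans an unpaired chi-square of baseline against follow-up in the same people, and loses power by it.** The SAP never says this. Pre-post comparison has its own sentence, with paired tests. The chi-square could equally compare attendance quartiles or baseline subgroups. No cut-point for social function is given, so no loss of power can be attributed to the plan.
- **That five rival tests compete for the main outcome.** The baseline and multilevel sentences can be read as features of the models. Two distinct contrasts then remain, which is why the figure given here is 9-10% and not higher.
- **That every listed method certainly applies to social function.** The remark about similar procedures directly follows the assumption checks and may refer only to them.
- **That the pilot shows pre-post change to be clearly significant.** This holds for attenders only if at least 25 were retested. Trailmaking A is also a cognitive test, not the main outcome, and attenders against non-attenders is not the SAP's quartile contrast.
- **That social function is undefined.** The protocol refers its objectives to separate information that was not supplied, and the definition may be there.

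It can also be said that the baseline rule covers models and that a chi-square test is not a model. That is fair, but it leaves a test named for the main outcome outside the SAP's own adjustment.

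None of this supplies a 6-month assessment, makes analysis of variance fit a categorical outcome, or says which contrast decides.

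**Conclusion.** The point holds, and the plan should be corrected. Two faults lie in the text and rest on no assumption: a 6-month time point that matches neither day 70-75 nor the 12-month records follow-up, and analysis of variance assigned to categorical outcomes. The third is an omission: neither the pre-post contrast nor the attendance contrast is primary. Its size, about 9-10% against 5%, rests on an assumed two-sided 0.05, n=300, independent participants and freedom to claim either result. The pilot figures show only that the two contrasts can point different ways. They do not predict what this trial will find.

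**What to change.** 1. Reconcile the 6-month time point with the day 70-75 assessment and the 12-month records follow-up.
2. Replace the chi-square and analysis-of-variance sentence with one primary contrast, pre-post or attendance. The choice is the investigators' and should be recorded before the data are analysed.
3. Name one model matched to the outcome type. For a score, use mean change with a unit random effect (pre-post), or ANCOVA of the follow-up score on attendance and baseline with a unit random effect (attendance). For a categorical outcome, use the mixed logistic or ordinal equivalent.
4. Label the other analyses supportive.
5. Name the social-function variable in the SAP only if the separate objectives do not define it.

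The cost is SAP wording and slightly more analysis work, with no new data. Confidence intervals will be somewhat wider than in an analysis that ignores units. How much wider depends on the number of units and the within-unit correlation, which the documents do not give. The SAP's own multilevel sentence already implies this cost.

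### If social function is analysed as a category, the chi-square and ANOVA named for the main outcome do not handle pairing or baseline, at a cost in power

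*SAP*

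**What the plan says.** The second paragraph of the SAP assigns a method to social function, which it calls the main outcome: χ² "tests and analysis of variance for categorical outcomes using data from baseline to 6 months". It does not say whether social function is a score or a category, or whether the tests compare time points or groups of patients.

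The same paragraph continues with:
- change over time: "Pre- to post-intervention (within-group) analyses will be performed using paired-sample" t-tests;
- attendance groups: "This will be done in quartiles and used to look at between group differences (analysis of covariance- ANCOVA");
- baseline: "Baseline score will be included as covariates in each model".

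The SAP closes with "Multilevel analysis will be used taking into account the included open care units", which is a level for units and not for repeated measurements within a patient.

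The protocol (Methodology) gives "Study design: Non randomized open trial" with no control group described, and "Our aim is to recruit 300 patients including mentors at each unit". Neither document names McNemar, Bowker, GEE or a patient-level mixed model. Neither gives an alpha, a power calculation or an assumed correlation between baseline and follow-up.

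**The concern.** With no control group described, baseline-to-follow-up data on social function are two measurements on the same people. The ordinary chi-square test and the ordinary analysis of variance assume independent observations. Applied to the two time points, they count each patient as two people. Measurements on one person are usually positively correlated, so the standard error of the change comes out too large and a real change may be missed.

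The other reading is a comparison of attendance groups at follow-up. Pairing is then not the issue, but a chi-square test has no place for a covariate, so it cannot meet the SAP's own statement about baseline.

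The later sentences do not close the gap for categories, because the paired t-test and ANCOVA are methods for a continuous response. Analysis of variance for a categorical response is also not a clear specification in itself.

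**Working it through.** The documents contain no power or error figure to reproduce. What follows is an illustration.

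**Inputs.** From the protocol: n = 300, a recruitment aim, taken here as 300 patients with both measurements. Assumed: two-sided alpha 0.05; proportion with a problem p₁ = 0.33 at baseline and p₂ = 0.25 at follow-up; within-patient phi 0.3 to 0.6, with 0 as a reference; no clustering by unit.

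**Type I error of the unpaired test.** With no true change, the variance of the difference is 2p(1−p)(1−φ)/n, while the unpaired test uses 2p(1−p)/n. True type I error is therefore 2[1 − Φ(1.96/√(1−φ))].
- φ = 0.3: 1.96/0.837 = 2.343, giving 0.019.
- φ = 0.6: 1.96/0.632 = 3.099, giving 0.0019.

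**Power.** Share with a problem at both times: p₁₁ = p₁p₂ + φ√(p₁(1−p₁)p₂(1−p₂)) = 0.0825 + 0.2036φ. Discordant shares: b = p₁ − p₁₁ and c = p₂ − p₁₁. The difference is b − c = 0.08.
- True SE = √{[b + c − (b−c)²]/n}.
- McNemar null SE = √{(b+c)/n}.
- Unpaired null SE = √{2 × 0.29 × 0.71/300} = 0.0370, the same for every φ.
- Power = Φ[(0.08 − 1.96 × null SE)/true SE].

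At φ = 0.3: p₁₁ = 0.1436, b = 0.1864, c = 0.1064, true SE = 0.0309 and McNemar null SE = 0.0312. McNemar power is Φ[(0.08 − 0.0612)/0.0309] = Φ(0.61) = 73%. Unpaired power is Φ[(0.08 − 0.0726)/0.0309] = Φ(0.24) = 59%.

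| φ | McNemar power | Chi-square power | Chi-square true type I error |
|---|---|---|---|
| 0 | 58% | 58% | 5.0% |
| 0.3 | 73% | 59% | 1.9% |
| 0.4 | 79% | 60% | 1.1% |
| 0.5 | 86% | 61% | 0.6% |
| 0.6 | 92% | 62% | 0.2% |

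Simulation (20,000 multinomial draws per setting) gave 73%, 80%, 87% and 93% for McNemar and 59–62% for chi-square at φ = 0.3 to 0.6, within about one percentage point of the formulas. At φ = 0 the two tests agree, so the loss comes from the ignored correlation alone.

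**Attendance-group reading.** No rate is needed here. The SAP requires the baseline score in each model, and a chi-square test on a group-by-category table has no covariate. The two statements cannot both be carried out for a categorical outcome.

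**The case against.** The strongest reply is that the paragraph must be read whole. It gives paired t-tests for change over time, and ANCOVA with baseline for attendance groups. The references to a baseline score, normality checks, Levene's test and Hedges' g all fit a continuous measure, and the protocol lists WHODAS 2.0 for overall function. A chi-square-type test could be meant to include McNemar, and analysis of variance could mean the repeated-measures form. All of this stands as far as it goes. For a score, pairing and baseline are handled. For a category, no paired form is named, and the one sentence that assigns a method to the main outcome speaks of categories.

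Three stronger readings are tempting but unsupported:

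- A reader might infer that the trial's main analysis is simply wrong, or that its error bars are. The text does not say that the tests would be applied in unpaired form, or that social function is a category. The harm is conditional on both.
- A reader might infer a risk of false claims of benefit from this choice of test. With positive correlation the error runs the other way.
- A reader might link this to the pilot, where "33 persons reported difficulties with social contacts while at the end of the intervention 17 of those reported no problems", and infer that only improvements will be counted. That is background reporting. Nothing in the SAP carries one-directional counting into this trial, and the protocol says that social contact will be measured more extensively here.

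**Conclusion.** The concern holds in conditional form. If social function, or any item of it, is analysed as a category, the SAP has no stated method that respects pairing when time points are compared, and none that carries baseline when attendance groups are compared. On the first reading, under the assumptions above, an ordinary chi-square test would run at a true type I error of about 2% to 0.2% and have roughly 60% power where a paired test has 73–93%. These figures depend on the assumed 33% and 25%, on phi, and on complete follow-up of 300 patients; with no within-patient correlation the loss vanishes. On the second reading the calibration problem does not arise, and what remains is the conflict with the SAP's own rule on baseline. For a continuous score there is no defect of this kind.

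**What to change.** - State whether social function is analysed as a score, a category or both.
- For a score, say that the paired and baseline-adjusted analyses already named apply.
- For categorical items, replace chi-square and ANOVA. For change over time, use McNemar (Bowker for more than two categories), or a logistic or ordinal mixed model with random effects for patient and unit. The mixed model also meets the SAP's commitment to account for units, which McNemar alone does not.
- For attendance groups, use logistic or ordinal regression of the follow-up category, adjusted for the baseline category.
- Report the change in proportion with a paired 95% confidence interval.

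The cost is a rewrite of one SAP sentence. No new data are needed, and no visit or instrument changes.
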